Effects of a Cognitive Interference Task on Alcohol Craving and Consumption Among Women

NCT number NCT04924283
Document Date 02/15/2022

Effects of a Cognitive Interference Task on Alcohol Craving and Consumption among Women ([name], Assistant Professor, Dept. of Psychiatry)

Despite the prevalence and serious consequences of alcohol use disorder (AUD) among women, only 5.4% receive treatment.¹ Brief mobile interventions are a promising way to deliver accessible, evidence-based interventions to women who would not otherwise seek help. The primary objective of the proposed study is to test the effects of a brief, cognitive interference task (Tetris) in reducing alcohol craving and consumption among women with at-risk drinking according to NIAAA guidelines.³ Elaboration Intrusion Theory (EIT) proposes that visual working memory processes are central to craving, and that imagined experiences of engaging in substance use increases motivation to engage in the actual behavior.⁴ In laboratory and real-world settings, participants report decreased craving for food and substances after completing Tetris, a visuospatial task that increases the demands of working memory processes.⁵⁻⁶ Based on previous research, the current study will collect ecological momentary assessment (EMA) data for a 1-week baseline period, followed by a 2-week intervention phase in which participants will be randomly assigned to the experimental condition (Tetris) or a control condition (assessment only). During the intervention phase, participants will receive a combination of event- and signal-contingent EMA assessments, and the experimental condition will also receive daily prompts to complete Tetris in-between assessments. EMA will be used to assess alcohol craving and consumption during the baseline and intervention phase and deliver the intervention in real-time.

Specific Aim 1: Evaluate the effects of a brief cognitive interference task on alcohol craving among women who report at risk drinking. Hypothesis: Participants in the experimental group, relative to controls, will evidence significantly lower craving 1) immediately after completing the task, and 2) during the 2-week intervention phase.

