EMA Assessment Period: The current study will employ a 1-week baseline EMA period followed by a 2-week experimental EMA protocol that uses a combination of event- and signal-contingent assessments. Based on previous EMA research, participants will be instructed to initiate a morning assessment each day to assess behaviors that may not have been captured during the in-vivo assessments the previous evening (*“How many alcohol drinks did you consume yesterday?; How many alcohol drinks do you plan to consume today?”*)¹⁰. They will be provided with examples of standard drinks to help accurately assess their drinking. In addition, participants will complete the imagery subscale from the Craving Experience Questionnaire (CEQ)¹¹ to retrospectively measure their strongest episode of craving during the previous day. Participants will also be prompted once per day to complete a Cue Reactivity Ecological Momentary Assessment (CREMA). CREMA provides real-time responses to alcohol-related stimuli presented in participant’s natural environment. Participants will be randomly prompted between 2:00-9:00 PM to begin a CREMA session. Participants will have 60 minutes to respond to the prompt. Participants will complete baseline measure of craving, stress and mood, and then view a photograph of an alcoholic beverage. Each item will be presented for 30 seconds. Different photographs will be presented at each study trial. After viewing the photograph, participants will be complete post ratings of their craving, stress and mood.

Between the hours of 2:00 p.m. and 9:00 p.m., participants will receive up to three random text message prompts to complete in-vivo assessments assessing craving and mood including: “How many standard drinks have you consumed since your last assessment?; “Are you drinking alcohol right now?; “How is your mood right now?; “How stressed do you feel right now.” “How strong is your craving for alcohol right now...” An automated text message system will be used with at least 1-hour between assessments and will de-activate after an hour has expired. Participants who responded to at least 80% of the morning assessments will be invited to continue participation in the experimental portion of the study.

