During, the experimental phase, the same assessments will be administered. In addition, any occasion in which a positive response to current craving is reported, an automated prompt will be displayed to re-rate cravings four minutes later. Participants in the experimental condition will receive an automated prompted to complete the Tetris task in-between the ratings. After four minutes the application will upload a screen shot of the Tetris game into RedCAP. The Tetris task involves manipulating basic shapes to form rows that then disappear. Participants in the experimental condition will be asked to play Tetris after CREMA sessions and after any of the three random craving assessment that participants report experiencing craving. Participants in the control condition will just be asked to re-rate craving four minutes later and report what activities they completed during the three-minute break.

Post-Experiment Assessment: Participants will complete self-report questionnaires via REDCap. In addition, participants will complete the TLFB over a video call at a 1-month follow-up. Figure 1 below illustrates the study design.

Figure 1. Study design

Statistical Analyses

To establish feasibility, descriptive analyses will be used to measure the proportion of prompts participants respond to, and the response time to complete prompts. An intent-to-treat analysis will be conducted with mixed-effects regression to test between-group differences in urge to drink after completing the task, nested within individuals. We will use a random-effects mixed modeling approach using maximum likelihood estimation to test differences in mean craving and drinking outcomes (i.e., alcohol consumption) between baseline and post-experiment. We will test differences in alcohol consumption between baseline and one-month follow-up. Participants will be modeled as random factors and the group allocation will be a fixed factor. Maximum likelihood estimation will provide unbiased estimates assuming missingness at random.¹³

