Descriptive analyses will be used to describe the sample. Clinical outcomes of interest are defined as: (1) decrease in craving measured by a single item from the Visual Analogue Scale immediately after task completion and from baseline to 2-week intervention phase (2) decrease in number of standard drinks (amount) from baseline to 2-week intervention phase and at 1-month follow-up measured by daily reports of “how many standard drinks did you consume yesterday?”. In order to establish feasibility, descriptive analyses will be used to measure the proportion of prompts participants responded to and response time to complete prompts. Intent to treat mixed-effects regression will be conducted to test differences in craving items after completing the task, nested within individuals. We will use a random effects mixed modeling approach using maximum likelihood estimation to test differences in mean craving and drinking outcomes (i.e., alcohol consumption) between baseline and post-experiment. We will also test differences in alcohol consumption between baseline and one-month follow-up. The participants will be modeled as random factors and the group allocation will be a fixed factor. We will examine the intervention between intervention and study time (baseline versus follow-up). Maximum likelihood estimation will provide unbiased estimates assuming missingness at random. [name] will be attending a summer statistical workshop in ecological momentary assessment data analysis and receive consultation from statisticians housed within the South Carolina Clinical & Translational Research Institute to support the proposed analyses in this project.

STUDY TIMELINE

| Overview of Study Timeline | | Months | | | | |
|-------------------------------------|--|--------|---|------|----|-----|
| | | 1 | 2 | 3-11 | 12 | 13+ |
| Tasks/Activities | | | | | | |
| Study Start Up | | ↔ | | | | |
| Recruitment | | | ↔ | → | | |
| Conduct Randomized Controlled Trial | | ↔ | → | | | |
| Data Cleaning/Analysis | | | ↔ | → | | |
| Dissemination | | ↔ | → | | | |

References

- ¹Substance Abuse and Mental Health Services Administration (SAMHSA). National Survey on Drug Use and Health (NSDUH). 2015 (NSDUH-2015-DS0001) Public-Use File Dataset. Available at: <https://www.datafiles.samhsa.gov/study-dataset/national-survey-drug-use-and-health-2015-nsduh-2015-ds0001-nid16894>.

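### The baseline versus 2-week comparisons have no stated row unit and no random phase effect; a random intercept fitted to EMA records can exceed the 5% level, mainly for craving

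*Combined protocol and SAP*

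**What the plan says.** The analysis is described twice, in Statistical Analyses (under Approach) and in Statistical Design and Power. Both propose a mixed model by maximum likelihood to "test differences in mean craving and drinking outcomes (i.e., alcohol consumption) between baseline and post-experiment". The random structure is one sentence in each place: "The participants will be modeled as random factors and the group allocation will be a fixed factor" in the later section, and the same without its first word in the earlier one.

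Three further statements bear on the comparison:

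- The outcome definitions in Statistical Design and Power run from baseline to the 2-week intervention phase for both outcomes. For drinks the wording is "from baseline to 2-week intervention phase and at 1-month follow-up measured by daily reports of", followed by the daily question.
- The only interaction sentence is "We will examine the intervention between intervention and study time (baseline versus follow-up". It appears to mean group by time, but it names follow-up, not the 2-week phase.
- The only nesting statement belongs to the separate post-task model, which is to "test differences in craving items after completing the task, nested within individuals".

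Neither section states the row unit, a random slope for phase, a residual correlation, a robust standard error or a degrees-of-freedom method for the phase comparison. The data-management text refers the reader back to the statistics section for the detailed plan, so nothing elsewhere fills the gap.

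**The concern.** Each woman supplies many records in each phase: a morning drinks report every day and up to three random craving prompts a day, plus a cue session. The simplest reading of participant as the random factor, applied to those records, is a random intercept. That model removes stable differences in level between women but assumes that every woman in an arm has the same true change. If changes differ, the variation belongs in the standard error of the group-by-phase effect, and a random intercept leaves most of it out. More records per woman make the omission worse, so craving is more exposed than drinks.

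Craving and consumption are the primary outcomes. Specific Aim 1 predicts that the experimental group, "relative to controls, will evidence significantly lower craving 1) immediately after completing the task, and 2) during the 2-week intervention phase". With 32 expected completers, two analysts following the same text could reach different conclusions on the second part of that hypothesis.

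**Working it through.** **Inputs from the documents.** Alpha is .05 (two-sided assumed, as sidedness is not stated). There are 32 expected completers, so 16 per arm at 1:1. Phases last 7 and 14 days.

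**Assumptions.**
- r = SD of women's true change ÷ residual SD of a record, taken as 0 to 0.5. The documents give no variance components.
- Craving: three prompts a day at 75% response. 3 × 7 × 0.75 = 15.75 and 3 × 14 × 0.75 = 31.5, so 16 and 32 records. In the plan 75% is a bonus threshold, not a forecast.
- Drinks: 7 and 14 reports at full response. A second case uses 6 and 12. The rule "Participants who responded to at least 80% of the morning assessments will be invited to continue" implies at least 6 of 7 baseline mornings (0.8 × 7 = 5.6); the 12 is assumed, because no such rule covers the intervention phase.

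**Random intercept on independent records.** Set the residual variance to 1. For n1 and n2 records, one woman's change has model variance V = 1/n1 + 1/n2 but true variance r² + V. With no group effect, the rejection rate is about 2 × [1 − Φ(1.96 × √(V/(r² + V)))].

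Worked case, drinks 7/14, r = 0.5: V = 1/7 + 1/14 = 0.2143; r² + V = 0.4643; √(0.2143/0.4643) = 0.679; 1.96 × 0.679 = 1.332; rate 18.3%.

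Worked case, craving 16/32, r = 0.5: V = 0.09375; r² + V = 0.34375; root 0.522; 1.96 × 0.522 = 1.024; rate 30.6%.

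| r | Drinks 7/14 | Drinks 6/12 | Craving 16/32 |
|---|---|---|---|
| 0 | 5.0% | 5.0% | 5.0% |
| 0.1 | 5.5% | 5.5% | 6.2% |
| 0.2 | 7.2% | 6.9% | 10.1% |
| 0.3 | 10.0% | 9.3% | 16.2% |
| 0.5 | 18.3% | 16.6% | 30.6% |

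The formula is slightly high at large r, because the fitted residual variance absorbs a little of the change variance. In 20,000 balanced simulated null trials per setting, r = 0.5 gave 17.4% (7/14), 15.5% (6/12) and 30.0% (16/32).

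**Fitted mixed models.** In 300 maximum-likelihood fits at 7/14 and r = 0.5 (16 per arm, Wald z), the random intercept rejected in 18.3% and the model with a random phase slope in 6.0%. At r = 0 the rates were 6.0% and 5.7%. With 300 fits, the Monte Carlo standard error near 6% is √(0.06 × 0.94/300) = 1.4 points.

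**Dependence within a woman.** A stable personal weekday pattern, assumed to be 30% of within-woman variance, balances across whole weeks and lowers the rates. Over r = 0/0.1/0.2/0.3/0.5, drinks 7/14 gave 2.1/2.2/3.7/5.8/13.9% and craving 2.5/3.9/7.3/13.1/28.8%. The craving runs let each woman answer 55-95% of prompts and used a within-woman estimator in place of the full random-intercept fit.

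**One mean per woman per phase.** The group-by-phase test is then a two-sample comparison of 32 change scores. Maximum likelihood divides the residual sum of squares by 32 instead of 30, and a normal reference uses 1.96. The rate is P(|t on 30 df| > 1.96 × √(30/32)) = P(|t| > 1.898) = 6.7%. Simulation gave 6.2-7.1%.

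**Baseline-adjusted phase means.** With a t reference on 29 df, simulated rates under independent records were 4.9-5.2% at r = 0 to 0.5.

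**The case against.** The strongest reply is that the plan never commits to the model criticised. It speaks of mean craving and drinking outcomes, which fits one mean per phase; participants as random factors does not rule out a random phase slope; and the later time point is called post-experiment, a label used elsewhere for the end-of-study questionnaires. The interaction sentence may concern only the one-month comparison. All of this stands, and it makes the fault one of specification.

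A reader might infer that the planned test will exceed 5% whenever women differ in their change. The documents do not support that: they give no variance components, they do not fix the model, and the weekday-pattern runs fall below 5% at small ratios.

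A reader might also infer from the Aim 1 wording that only intervention-phase data would be compared, leaving the baseline week unused. The outcome definitions, which start from baseline, point the other way.

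The study is a pilot, and the plan provides for an EMA-analysis workshop and statistical consultation. That lowers the consequence but does not specify the model. The plan still states significance hypotheses and an aim of preliminary efficacy at alpha .05.

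**Conclusion.** The concern holds in conditional form. The text names participant as the only random factor and leaves the row unit open. On the record-level random-intercept reading, with independent records and assumed ratios of 0.1 to 0.5, the group-by-phase test rejects a true null in about 6-31% of trials for craving and 6-18% for drinks. At a ratio of 0.1 the excess is about one point or less; the upper ends need a ratio of 0.5. A stable weekday pattern can make the test conservative at small ratios. On the phase-mean reading the excess is small, 6-7%, and comes from maximum likelihood with a normal reference at 16 per arm. Normal outcomes are assumed in these figures. The same text thus permits tests with materially different error rates, and this should be settled before analysis.

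**What to change.** State that the tested term is group by phase, with baseline week versus 2-week intervention phase as the levels, and state the row unit. Then name one of these as primary in advance and the other as sensitivity:

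- (a) A record-level mixed model with a participant random intercept and a random phase slope, fitted by REML with Kenward-Roger or Satterthwaite degrees of freedom. This keeps the plan's mixed-model, missing-at-random approach. The checks above used maximum likelihood with a normal reference for this model; the REML version with small-sample degrees of freedom was not run.
- (b) Each woman's intervention-phase mean regressed on arm, adjusted for her baseline-phase mean, with a t reference.

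Say also whether cue-session ratings count towards craving.

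The cost is two or three sentences and no new data. Confidence intervals will be wider than from a random-intercept-only model when women differ in their change. Under (b), women with few records count equally unless weighted, and a woman with no intervention-phase record contributes no outcome.

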Specific Aim 2: Evaluate the effects of a brief cognitive interference task on alcohol consumption, as measured by self-report among women who report at risk drinking. Hypothesis: Participants in the experimental group, relative to controls, will demonstrate significantly lower consumption of alcohol (fewer standard drink units) during the 2-week intervention phase and at 1-month follow-up.

Approach

Participants: Forty women who report at risk drinking will be recruited nationally from online campaigns, the community, and locally from the Women's Health Clinic at the Medical University of South Carolina (MUSC). Many women use obstetricians and gynecologists (OB/GYN) as their primary resource for behavioral health care making OB/GYN health care settings an ideal place to provide accessible interventions for AUD to women.² The inclusion criteria for alcohol consumption will be having a positive score on the AUDIT-C (i.e., a score of 3 or greater) at the time of screening. Additional inclusion criteria include: 1) female, any race or ethnicity; 2) ages 21-65; 3) able to comprehend English to provide informed consent and complete the assessments. Exclusion criteria include: 1) currently engaged in treatment for AUD; 2) current clinically significant bipolar affective disorder, schizophrenia, or psychotic disorder; 3) pregnant; 4) imminently suicidal or homicidal; 5) participants taking medications known to affect alcohol craving or consumption and 6) a score of 10 or higher on the Clinical Institute of Alcohol Withdrawal Revised (CIWA-R).²⁴

Study Procedures

Initial Screening. Potential participants will complete a brief screener over the phone or via REDCap to determine initial eligibility. The brief screener will ask yes/no and multiple choice questions focused on inclusion/exclusion criteria.

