Upon enrollment, participants will be given a full description of study procedures and asked to sign an electronic IRB-approved consent form before any additional study procedures or assessments, aside from the initial screener, are conducted. E-consent will be completed on REDCap. Participants will be sent a link to review the e-consent. Research staff will review the consent form over the phone or teleconferencing and answer any questions. Participants will be given as much time as needed to review the consent form. Participants and staff will sign the form electronically. A PDF of the completed consent form will be emailed securely to participants. Participants will complete a baseline assessment, followed by an EMA assessment period, and a post-experiment visit. To decrease risk regarding COVID-19 and increase feasibility, all study procedures will be

conducted with via telemedicine. Vidyo or doxy.me video conferencing will be used. Participants will complete study measures via a REDcap link.

Baseline Visit: The baseline visit will include interview measures that will be completed on doxy.me or vidyo, and self-report surveys completed on REDcap. Self-report measures include items from the DIAMOND¹⁸ screener, the Alcohol Use Disorder Identification Test (AUDIT),⁸ the patient health questionnaire (PHQ-9)¹⁹ and Stages of Change Readiness and Treatment Eagerness Scale (SOCRATES),⁹ Life Experiences Questionnaire²⁰, Posttraumatic Stress Disorder Checklist for DSM-5 (PCL-5)²¹, Drinking Motives Questionnaire²², the Obsessive Compulsive Drinking Scale (OCD)¹², four items assessing COVID-19 related stress, and Short UPPS-P²³. Interview measures include the Time Line Follow [name] (TLFB),⁷ substance use modules of the DIAMOND, Treatment Services Review²⁵, and for participants who screen positive for mood disorders, psychotic disorders, or suicidality will receive the corresponding modules of the DIAMOND. Eligible participants will be instructed on how to complete ecological momentary assessments (EMAs), including instructions on how to measure a standard drink and report craving. Participants will be randomized to the experimental or control condition stratified by self-report craving and depression scores. Participants assigned to the experimental condition will be instructed on how to complete the Tetris task.

[figure not shown]

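### The models omit the two randomisation strata and a baseline covariate where craving is compared as a level; if the phase comparison uses daily or prompt records, a random intercept alone would not be enough

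*Combined protocol and SAP*

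**What the plan says.** The Baseline Visit paragraph under Study Procedures says that allocation is "stratified by self-report craving and depression scores". It gives no instrument, levels or cut-points for either score.

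The model is described twice. Statistical Analyses says "Participants will be modeled as random factors and the group allocation will be a fixed factor", and Statistical Design and Power repeats it: "The participants will be modeled as random factors and the group allocation will be a fixed factor". The second section adds what reads as a group-by-time interaction. Neither section names the strata, any other covariate, a random phase effect or a residual correlation structure, and neither rules them out.

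The outcomes are worded in two ways.
- **As levels.** Specific Aim 1 expects that the experimental group "will evidence significantly lower craving 1) immediately after completing the task, and 2) during the 2-week intervention phase". Specific Aim 2 says that it "will demonstrate significantly lower consumption of alcohol (fewer standard drink units) during the 2-week intervention phase". Statistical Analyses plans mixed-effects regression "to test between-group differences in urge to drink after completing the task".
- **As change.** Statistical Design and Power defines the first outcome as "decrease in craving measured by a single item from the Visual Analogue Scale immediately after task completion" and from baseline to the intervention phase, and defines drinking likewise as a fall from baseline.

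For the phase comparison the plan will "test differences in mean craving and drinking outcomes", yet drinking is measured by daily reports. It does not say whether the model takes single records or one mean per woman per phase.

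**The concern.** Stratified allocation makes the arms alike on craving and depression. A model without those factors still counts their variance as noise. If they predict the outcome, a comparison of levels then has too large an SE and a conservative test. With 32 expected completers, that precision is worth keeping.

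The random-effects wording raises a second question, which acts in the other direction. If single daily or prompt records are modelled with only a random intercept, real differences between women in how much they change are treated as record-level noise. The group-by-phase SE is then too small, which favours a false finding on craving or drinking, the two primary outcomes.

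**Working it through.** **Inputs from the documents.** 40 women randomised 1:1; 20% dropout, so 40 × 0.80 = 32 completers, which reproduces the plan's figure; d = .50; a 7-day baseline and a 14-day experimental phase; one morning report a day (7 + 14); four prompts a day (28 + 56). A plain two-sample t-test at d = .50 with 16 per arm has 27.8% power. The plan's total of 24 for 80% power is not a two-sample t-test figure; that is a separate matter and is not used here.

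**Assumptions, because the documents give no variances.** Between-woman SD 1, residual SD 1, 14 ratings per woman in the level comparison, and two binary strata that together explain a share R² of between-woman variance.

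**1. Strata, outcome compared as a level.** The variance of a woman's mean is 1 + 1/14 = 1.071 without the strata and 1.071 − R² with them. The SE ratio is √[(1.071 − R²)/1.071] × 1.009. The factor 1.009 is the simulated cost of estimating two more terms.
- R² = .10: .952 × 1.009 = .96
- R² = .20: .902 × 1.009 = .91
- R² = .30: .849 × 1.009 = .86

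Simulation (40 randomised in blocks of 4 within four cells, 8 lost at random, 12,000 runs per setting) agrees:

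| R² | SE ratio | Rejection under no effect, unadjusted / adjusted | Power at d = .50, unadjusted / adjusted |
|---|---|---|---|
| 0 | 1.009 | 5.2% / 5.1% | 27.4% / 27.0% |
| .10 | .959 | 4.4% / 5.1% | 27.1% / 29.4% |
| .20 | .908 | 3.6% / 5.0% | 25.4% / 31.1% |
| .30 | .854 | 2.8% / 5.0% | 25.2% / 35.7% |

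If d is instead read as 0.50 between-woman SDs, the adjusted SE is 1.009 × √[(1.071 − R²) × 2/16] = .352, .333 and .313. Then .50/SE is 1.42, 1.50 and 1.60, and power (t, 28 df) is 28%, 31% and 34%. With 5 ratings per woman the SE reduction is about 3%, 8% and 13%.

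**2. Strata, outcome compared as change.** A stratum effect that is the same in both phases cancels in post minus pre. The simulated SE ratio is 1.009 at every R², so there is no gain.

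**3. Baseline value as a covariate in a level comparison.** Take the mean of 7 baseline records, with variance 1 + 1/7. Let τ be the SD of true change between women. The remaining variance is 1 + τ² + 1/14 − 1/(1 + 1/7).
- τ = 0: 1.071 − .875 = .196; SE = √(.196 × 2/16) = .157; .50/.157 = 3.2; power about 87%.
- τ = .5: 1.321 − .875 = .446; SE = .236; .50/.236 = 2.1; power about 53%.

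Simulation gives about 86% and 51% on the same scale. If d is scaled by the total SD, it gives 87–89% and 63–65%. Adding the strata to the baseline mean leaves these figures essentially unchanged.

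**4. Phase comparison on single records, random intercept only.** Let n₀ and n₁ be the answered records per phase. The ratio of model SE to true SE is about √[A/(A + τ²)], with A = 1/n₀ + 1/n₁. The false-positive rate is 2 × [1 − Φ(1.96 × ratio)]. At τ = .25 residual SD:
- Daily reports, 7 + 14 at an assumed 90% response: A = 1/6.3 + 1/12.6 = .238; ratio .89; 8%.
- Prompts, 28 + 56 at an assumed 75% response: A = 1/21 + 1/42 = .071; ratio .73; 15%.

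Simulation gives 8.7% and 16.4%. At τ = 0 the rate is about nominal (4.3% and 4.5%). With a random phase effect it is 3.5–5.6% over τ from 0 to .50, and with one mean per woman per phase 4.6–5.8%. Serial correlation of .2 to .4 between daily records, with τ = 0, gives 13–21% under a random intercept alone and about 5% for the change in person means (150 fits per setting, so these are rough).

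**The case against.** The strongest objection is about reach. Statistical Design and Power, the fuller analysis text, defines its outcomes as decreases and compares baseline with the later phase. In that form the strata cancel. Only post-task craving, as worded in Statistical Analyses, is clearly a comparison of levels, and even that is called a decrease in the other section. This stands, and the point is limited accordingly. A reader of Aims 1 and 2 might infer that every primary analysis loses precision. The model text does not support that.

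A second objection is that the strata are the weaker covariate. This also stands: once the baseline-week mean is in the model, the strata add almost nothing under the assumptions used. The remedy therefore has to include both.

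Four stronger readings are tempting and should be resisted.
- That omitting the strata produces false claims. It makes the test conservative.
- That the plan commits to an intercept-only model on raw records. It never says so; its random-effects wording is general, and it speaks of mean outcomes.
- That the drinking analysis is a mis-specified count model. No count model appears in the plan.
- That maximum likelihood must be replaced by another estimator or a degrees-of-freedom correction. No comparison here shows that.

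Finally, this is a pilot, and the plan already foresees training in this type of data and consultation with statisticians. That makes the change easy, but it does not put the terms into the plan.

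**Conclusion.** The point holds in a limited form. The plan stratifies on craving and depression and names neither in its models. For a level comparison, clearly intended only for post-task craving, adjustment cuts the SE by about 4–15% and lifts power at d = .50 from about 25% to 28–36%, if the strata explain 10–30% of between-woman variance. It costs about 1% of the SE if they explain none. It does not make strata adjustment alone adequate: power stays low until the baseline value is used as well. How much baseline brings depends on how stable women are between phases, which the documents do not give.

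The second part is conditional. It needs record-level fitting, a random intercept alone, and either real differences in change between women or serial correlation. With one mean per woman per phase it does not arise. It is a gap to close before analysis, not an error that the plan has made.

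**What to change.** 1. State which craving and depression scores the randomisation uses, and with what levels.
2. In the post-task craving model, and in any intervention-phase craving or drinking model that compares levels, add both factors as fixed covariates in the form used for randomisation. Add the baseline value of the outcome too: the baseline-week mean, or the pre-task rating for post-task craving. The pre-task rating is taken after allocation, so a model that uses it estimates the immediate effect given craving at that moment; the text should say so.
3. State the unit of analysis for the phase comparison. Either use one mean per woman per phase, or, for daily or prompt records, add a participant-level random phase effect and allow for serial correlation.

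The cost is wording only, with no new data. Two binary strata take the residual degrees of freedom from 30 to 28, and the baseline covariate takes one more; strata with more levels take more. Intervals for the phase effect may widen, correctly. One mean per phase weights women equally despite unequal response, but the mixed model still keeps women observed in one phase only.
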